## 6.4.10 Safety Analysis

All safety data will be listed and tabulated. The analysis will be performed on the Safety population.

Safety parameters include adverse events, laboratory parameters, vital signs, ECG, physical examination findings, C-SSRS and DEQ-5 and VAS.

### **6.4.10.1** Clinical Laboratory Parameters

The clinical laboratory tests will be obtained at Screening, Day -1 of each treatment period, and end of study. The following laboratory evaluations will be performed.

Hematology	Serum Chemistry						
RBC Hematocrit Hemoglobin Mean corpuscular hemoglobin (MCH) Mean corpuscular volume (MCV) Mean corpuscular hemoglobin concentration (MCHC) Platelet count WBC count (with differential)	Creatinine Potassium (K+) Sodium (Na+) Chloride (Cl-) Magnesium (Mg++) Glucose Urea Bilirubin (Total) Bilirubin (direct)	eGFR AST ALT AP Total Protein Albumin CO 2					
Neutrophils (granulocytes) Lymphocytes Monocytes Basophils Eosinophils							

**Urinalysis:** Macroscopic examination routinely including specific gravity, pH, protein, glucose, ketones, blood and urobilinogen. A microscopic examination will be performed if warranted based on macroscopic results.

**Urine drug screen:** A urine sample will be collected and analyzed (positive or negative) for drugs of abuse including amphetamine, opiate, cocaine, barbiturates benzodiazepines, and marijuana (tetrahydrocannabinol [THC]).

For the Screening visit only, cotinine will be included in the urine drug screen panel.

**Serology:** Testing for HbsAg, Hepatitis C antibody and HIV 1 and 2 will be performed at the screening visit only. Results of each serology test will be reported as either positive or negative.

**For females:** A serum\_hCG test at the screening visit and EoS, urine\_hCG test on the day of Phase 1 unit admission for each of the three treatment periods (Day -1 of each dosing period).

AST: aspartate aminotransferase; ALT: alanine aminotransferase; AP: alkaline phosphatase; HbsAg: hepatitis B surface antigen; hCG: human chorionic gonadotropin; HIV: human immunodeficiency virus; RBC: red blood cell; WBC: white blood cell

Laboratory test results for Clinical Chemistry, Hematology and Urinalysis, will be listed and summarized descriptively by treatment and visit. There will be no change from baseline calculations performed for Laboratory data.

**Breathalyzer Test-** The breathalyzer assessment for breadth alcohol concentration will be performed at Screening and Day-1 of each dosing period. A by subject listing of the data will be generated.

All individual subject clinical laboratory test results will be presented in listings by period, subject and visit.

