#### Safety:

All randomized subjects who receive at least one dose of study drug will be included in the safety and baseline analyses.

The safety analysis will evaluate adverse events and additional safety parameters. The number and percentage of subjects experiencing at least one adverse event will be summarized by body system, preferred term, and treatment. If appropriate, adverse events will also be summarized by intensity and relationship to study drug. Serious adverse events, if any, will be tabulated.

Additional safety parameters will be assessed from summaries of physical examinations, 12-lead ECGs and vital signs. The 12-lead ECG results will be categorized as normal, clinically significant abnormal, and not clinically significant abnormal. Hematology, chemistry and urinalysis laboratory test results will be categorized as low, normal, or high relative to the normal ranges and values outside the normal range will be assessed for clinical significance. The changes from baseline for each of these parameters at post-dose time points will be presented.

Table 1. Schedule of Events (Overview)

	Screening Visit 1	Dos	sing Perio	d 1	De	osing Peri Visit 3	od 2	D	osing Period Visit 4	13	EoS Visit 5
Day	-21 to -1	-1	1	2	-1	1	2	-1	1	2	21 (+/- 2)
In-house		X	Х	X	Х	Х	X	X	X	Х	1
Outpatient	Х										Х
Informed consent	X										
Eligibility/Confirm continued eligibility	X	Х			Х		1 3 16	Х			
Demographics, Body Weight, Height, Calculate BMI	Х						Appen				1, 7
Medical history review/update	Х	X			Х			X			
Complete physical examination 	Х										X
Targeted physical exam (symptom related, if applicable)		Х	х	Х	Х	х	Х	Х	X	Х	
Urine screen for drugs of abuse  and Breathalyzer test	х	Х			X			Х			
Hepatitis B/C and HIV-Screen	X						N 7 - 3				
Serum pregnancy test 	Х						2 3 3 5		177 1		X
Urine pregnancy test 		Х			Χ.		E 1 4 H	X			
12-lead ECG⁴	Х		X	X		X	Х		X	Х	X
Vital signs (BP, HR, RR and oral temperature) 	х	Х	Х	Х	Х	Х	X	Х	×	Х	Х
Orthostatic Vital signs (BP and HR) 	х		х			х	E 1 4 4	717	Х		
Clinical Laboratory Tests (CBC, Chemistry, Urinalysis)	х	Х			Х		1999	Х			×
Training on VAS instruments 		X			Х		E 1 7 1	X			
Bipolar Drug liking VAS			Х			Х		- 2 5	Х		
Bipolar High VAS			Х			Х			X		
Unipolar Sedation VAS			Х			Х	4 6		X		
DEQ-5			Х	Х		Х	X	B 1 E	Х	X	
Unipolar Overall drug liking VAS			X	Х		Х	X	712	X	X	

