## 7.11 Clinical Laboratory

### 7.11.1 Laboratory Parameters

Laboratory testing (hematology with differential, serum chemistry and urinalysis) will be performed using standard methods.

All subjects must fast at least 8 hours prior to any clinical laboratory assessment blood draw.

The urine screen for drugs of abuse will be performed at Screening and on Day -1 of each dosing period at check-in. Hepatitis B/C and HIV serology will be performed at Screening. Serum pregnancy testing will be done on all female subjects at Screening and EoS. Urine pregnancy testing will be completed on all female subjects on Day -1 of each dosing period at check-in. Clinical laboratory testing (CBC, chemistry, and urinalysis) will be performed at Screening, Day -1 of each dosing period, and EoS.

Table 3: List of Laboratory Tests

Hematology	Serum Chemistry	
RBC Hematocrit Hemoglobin Mean corpuscular hemoglobin (MCH) Mean corpuscular volume (MCV) Mean corpuscular hemoglobin concentration (MCHC) Platelet count WBC count (with differential) Neutrophils (granulocytes) Lymphocytes Monocytes Basophils Eosinophils	Creatinine Potassium (K+) Sodium (Na+) Chloride (CI-) Magnesium (Mg++) Glucose Urea Bilirubin (Total) Bilirubin (direct)	eGFR AST ALT AP Total Protein Albumin CO 2

**Urinalysis:** Macroscopic examination routinely including specific gravity, pH, protein, glucose, ketones, blood and urobilinogen. A microscopic examination will be performed if warranted based on macroscopic results.

**Urine drug screen:** A urine sample will be collected and analyzed (positive or negative) for drugs of abuse including amphetamine, opiate, cocaine, barbiturates benzodiazepines, and marijuana (tetrahydrocannabinol [THC]). For the Screening visit only, cotinine will be included in the urine drug screen panel.

**Serology:** Testing for HbsAg, Hepatitis C antibody and HIV 1 and 2 will be performed at the screening visit only. Results of each serology test will be reported as either positive or negative.

For females: A serum\_hCG test at the screening visit and EoS, urine\_hCG test on the day of Phase 1 unit admission for each of the three treatment periods (Day -1 of each dosing period).

AST: aspartate aminotransferase; ALT: alanine aminotransferase; AP: alkaline phosphatase; HbsAg: hepatitis B surface antigen; hCG: human chorionic gonadotropin; HIV: human immunodeficiency virus; RBC: red blood cell; WBC: white blood cell

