### 8.6.2 Clinical Laboratory

Clinical laboratory values will be summarized by descriptive statistics by treatment (lasmiditan 200 mg co-administered with sumatriptan (lmitrex) 100 mg, lasmiditan 200 mg co-administered with lasmiditan placebo 200 mg, or sumatriptan (lmitrex) 100 mg co-administered with lasmiditan placebo 200 mg). Changes from baseline in clinical laboratory values will be summarized by descriptive statistics. All clinical laboratory values outside normal range (including Screening and EoS examination) will be listed by treatment (lasmiditan 200 mg co-administered with sumatriptan (lmitrex) 100 mg, lasmiditan 200 mg co-administered with lasmiditan placebo 200 mg, or sumatriptan (lmitrex) 100 mg co-administered with lasmiditan placebo 200 mg) and subject number, including demographic information and flagging of values.

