## Vital Signs/Orthostatic Vital Signs

Vital signs will be obtained at Screening, Day -1, Day1 (predose, 1hr, 2hr, 4hr, 8hr, 24hr post dose) and Day 2 of each period.

Vital signs will include body temperature, respiratory rate, heart rate and systolic and diastolic blood pressure.

Orthostatic vital signs will be obtained at Screening and Day 1 (predose, 1hr, 2hr) of each period and may or may not include all the vital parameters.

Height, weight and BMI will be measured only at the Screening Visit only.

Actual values of vital signs and changes from baseline will be summarized using descriptive statistics by treatment and time point. Only subjects with both non-missing baseline and time point values will be summarized at each time point.

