### 6.4.10.2 Electrocardiogram (ECG)

ECG will be obtained at Screening, Day 1 (predose, 1hr, 1.5hr, 2hr, 2.5hr, 4hr, 8hr) Day 2 (24hr) of each treatment period and end of study.

Standard 12-lead ECGs evaluations will include heart rate and interval information such as RR, PQ/PR, QRS, QT, QTcF and QTcB. Overall interpretation (normal, abnormal not clinically significant or abnormal clinically significant) will also be recorded.

For continuous ECG parameters, actual values and changes from baseline will be summarized using descriptive statistics by treatment and time point. For ECG interpretation, the number and percentage of subjects will be summarized by treatment and time point. Additionally, a shift table from baseline to Day 2 will be presented for each treatment.

All ECG data will be provided as a by-subject listing.

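### SAP 6.4.10.1 cancels, without a reason, the laboratory change-from-baseline summary planned in protocol 8.6.2, and leaves a by-treatment table with no scheduled post-dose values except possibly EoS

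*SAP*

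**What the plan says.** **Protocol.** Section 8.6.2 summarises laboratory values by treatment and adds: "Changes from baseline in clinical laboratory values will be summarized by descriptive statistics". It also plans a listing: "All clinical laboratory values outside normal range (including Screening and EoS examination) will be listed by treatment". The synopsis, under Safety, says "Hematology, chemistry and urinalysis laboratory test results will be categorized as low, normal, or high relative to the normal ranges", and then, after mentioning physical examinations, ECGs and vital signs as well as laboratory tests, "The changes from baseline for each of these parameters at post-dose time points will be presented". The synopsis is the less direct support, because that sentence covers several kinds of data. Section 7.11.1 fixes the sampling: "Clinical laboratory testing (CBC, chemistry, and urinalysis) will be performed at Screening, Day -1 of each dosing period, and EoS".

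**SAP.** Section 6.4.10.1 repeats the sampling times and says results will be listed and "summarized descriptively by treatment and visit. There will be no change from baseline calculations performed for Laboratory data". It mentions neither the low/normal/high categories nor the out-of-range listing. For the other safety measurements the SAP keeps the change summary. For vital signs: "Actual values of vital signs and changes from baseline will be summarized using descriptive statistics by treatment and time point". For ECG: "For continuous ECG parameters, actual values and changes from baseline will be summarized using descriptive statistics by treatment and time point".

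**Baseline.** SAP Sections 5 and 6.1 define baseline separately for each period, as the last value before that period's dose, and compute change inside the period.

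**The concern.** There are two linked problems.

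First, the SAP removes a summary that the protocol plans. The SAP's introduction presents it as the detailed specification of the protocol's analysis, yet here it takes something out and does not say why. Vital signs and ECG keep the same summary, so this is not a general simplification.

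Second, the table that remains cannot do the work. It is organised by treatment, but the only laboratory value scheduled inside a dosing period is taken before the dose. Laboratory parameters are part of the secondary safety endpoint in the synopsis, and that part would not be answered by treatment. The samples that could answer it exist, at the next period's Day -1 and at EoS. The SAP neither links them to the treatment just taken nor compares them with anything.

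**Working it through.** No power or alpha figure is involved. The check sets the two texts side by side and counts which samples fall where.

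**Inputs**
- Dosing on study Days 1, 8 and 15; Day -1 of Periods 2 and 3 on study Days 7 and 14; EoS on Day 21 ± 2 (protocol 3.1 and Table 1).
- Laboratory samples at Screening, each period's Day -1 and EoS (protocol 7.11.1, SAP 6.4.10.1). Both detailed schedules show none between dose and discharge.
- Six sequences with 7 subjects each, 42 in all (protocol 5.6).
- At least 36 completers (protocol 8.1).

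**Step 1: lag from dose to next scheduled sample**
- Period 1: 7 − 1 = 6 days.
- Period 2: 14 − 8 = 6 days.
- Period 3: 21 − 15 = 6 days, with a range from 19 − 15 = 4 to 23 − 15 = 8 days.

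Post-dose samples therefore exist for every period, but none lies inside its dosing period.

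**Step 2: content of the SAP's table, 42 completers**

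Each treatment stands in each period in 2 of the 6 sequences, so 2 × 7 = 14 subjects receive it in each period. Its Day -1 row holds 3 × 14 = 42 values, all taken before that treatment is given. Of these, 14 (Period 1) follow no study drug and 28 (Periods 2 and 3) were taken 6 days after a different treatment. EoS adds 14 values per treatment only if it is assigned to the Period 3 treatment.

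**Step 3: change values available per treatment**

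| Rule | 42 completers | 36 completers |
|---|---|---|
| SAP as written | 0 | 0 |
| Cancelling sentence deleted, within-period rule kept, EoS counted in Period 3 | 14 | 12 |
| Most recent treatment, against that period's Day -1 | 28 + 14 = 42 | 24 + 12 = 36 |

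Over the three treatments the last row gives 3 × 42 = 126, or 3 × 36 = 108. The 12 and the 24 + 12 split assume 6 completers per sequence. The total of 36 does not, because every completer takes all three treatments. The 42 − 36 = 6 planned non-completers could add some Day -1 or early-termination values, which the 36-completer column leaves out.

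The middle row shows that deleting the sentence alone is not enough. Without an assignment rule, the samples after Periods 1 and 2 still go unused.

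**The case against.** The best defence of the SAP is that its choice is sensible. With change computed inside each period and no sample between dose and discharge, there is almost nothing to compute. Protocol Section 8 also allows departures from the planned analyses if the study report justifies them. That stands as far as it goes: a reasoned decision to drop the summary would settle the conflict. But the SAP states no reason, and the treatment for EoS and early-termination samples would still be undefined.

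The weight is also fairly disputed. Abnormal results are classed for clinical significance (protocol 7.11.3), clinically relevant changes can be recorded as AEs (7.14.1), and the SAP lists every subject's results. No test or decision rule uses the table. All of this stands. A reader might infer that laboratory safety goes unmonitored; the documents do not support that.

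Three other stronger readings also fail.
- **A 67% error rate.** Since 28 of 42 Day -1 values per treatment (67%) follow another treatment, a reader might call them mislabelled. They are not: under SAP Sections 5 and 6.1 a Day -1 row is a correctly labelled baseline for its own period.
- **Day -1 undefined.** Those same definitions largely settle Day -1. The open cases are EoS, early-termination and unscheduled samples.
- **126 planned values lost.** Protocol 8.6.2 does not say that the changes are by treatment and names no reference value. One change per subject from before the study to EoS, 42 in all, would satisfy its sentence. The 126 comes from the rule proposed here.

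Finally, the missing assignment rule is inherited from protocol 8.6.2, which also tabulates by treatment without one. The SAP is where it should be supplied.

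**Conclusion.** The conflict between SAP 6.4.10.1 and protocol 8.6.2 is explicit and unexplained. As written, the SAP yields no laboratory change values and a table whose scheduled entries are pre-dose values for each treatment, apart from 14 EoS values per treatment if EoS is assigned to Period 3.

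The proposed rule would give up to 42 change values per treatment with 42 completers, and 36 with 36 before any contribution from non-completers. These counts assume nominal visit days and one scheduled sample after each dose.

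The consequence is confined to a descriptive secondary safety table, with individual review and listings intact. It is a correction the sponsor should make, at the low end of priority.

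**What to change.** In SAP 6.4.10.1:

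1. Delete the sentence that cancels change from baseline, so that the SAP agrees with protocol 8.6.2.
2. Label Day -1 as the baseline of its own period, and show Screening without a treatment.
3. For the change and low/normal/high shift summaries, assign every sample taken after a dose and before the next one (next Day -1, EoS, early-termination, unscheduled) to the most recent treatment. Measure it against the Day -1 value of that treatment's period. State that this is an exception to the within-period rule in SAP Sections 5 and 6.1.
4. Carry the out-of-range listing from protocol 8.6.2 into the SAP and apply the same rule to it.

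The cost is a few sentences and one visit-to-treatment mapping step in programming, with no extra samples. Two limits should be stated beside the table. Scheduled samples come about 4 to 8 days after a single dose, so early transient effects are missed. Day -1 of Periods 2 and 3 serves both as the outcome of one treatment and as the baseline of the next. Relabelling removes neither.

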### 6.4.10.2 Electrocardiogram (ECG)

ECG will be obtained at Screening, Day 1 (predose, 1hr, 1.5hr, 2hr, 2.5hr, 4hr, 8hr) Day 2 (24hr) of each treatment period and end of study.

Standard 12-lead ECGs evaluations will include heart rate and interval information such as RR, PQ/PR, QRS, QT, QTcF and QTcB. Overall interpretation (normal, abnormal not clinically significant or abnormal clinically significant) will also be recorded.

For continuous ECG parameters, actual values and changes from baseline will be summarized using descriptive statistics by treatment and time point. For ECG interpretation, the number and percentage of subjects will be summarized by treatment and time point. Additionally, a shift table from baseline to Day 2 will be presented for each treatment.

All ECG data will be provided as a by-subject listing.

## 6.4.10.3 Physical Examination

Complete physical examination will be performed at Screening and end of study. A brief targeted physical examination will be performed if indicated by an AE during each dosing period.

Physical examination will include the assessment of general appearance, head, eyes, ears, nose, throat (HEENT), thyroid (endocrine), heart, chest, lungs, abdomen, skin, neurological, extremities, and back. Each body system will be assessed as normal, abnormal not clinically significant or abnormal clinically significant.

Physical examination findings will be summarized by visit and body system. The number and percentage of subjects with normal, abnormal not clinically significant and abnormal clinically significant findings will be presented for each body system.

All physical examination data will be provided in a listing.

#### 6.4.10.4 Columbia Suicide Severity Rating Scale (C-SSRS)

C-SSRS will be performed at screening with the screening/baseline version of the form. The 'Since last visit' version would be used in each dosing period at Day-1, Day 2 and end of study. A by subject listing and summary table for C-SSRS will be generated only for positive responses to any questions in the C-SSRS. If there are no positive responses, there will be a line indicating 'None of the study subjects responded with a positive response' for the listing and summary table.

### 6.4.10.5 Visual Analogue Scale (VAS)

VAS scales will be administered on 100mm scales as per the protocol. The following VAS scales will be performed and subjects will be trained on Day-1 of each period.

- 1. Bipolar drug liking
- 2. Bipolar High VAS
- 3. Unipolar sedation
- 4. Unipolar overall drug liking VAS
- 5. Unipolar take drug again VAS

All VAS data will be provided as a by-subject listing and summarized by period, treatment and visit.

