#### Secondary Endpoints:

- The pharmacokinetic (PK) parameters of lasmiditan 200 mg when given with sumatriptan (Imitrex) 100 mg.
- The safety and tolerability of lasmiditan 200 mg as defined by adverse events, laboratory parameters, vital signs and electrocardiograms (ECGs) when given with sumatriptan (Imitrex) 100 mg.

**Exploratory Endpoint:** The subjective drug effects of lasmiditan 200 mg when given with sumatriptan (Imitrex) 100 mg as compared with either drug alone and as measured by results of the VAS scales and the DEQ-5.

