# 5.6 Randomization and Blinding

This is a randomized, double-blind, three-period, cross-over, study to investigate the effect of single doses of sumatriptan (Imitrex) 100 mg on the pharmacodynamics of a single dose of lasmiditan 200 mg. The dosing periods are:

- A: Lasmiditan 200 mg co-administered with lasmiditan 200 mg placebo
- B: Sumatriptan (Imitrex) 100 mg co-administered with lasmiditan 200 mg placebo
- C: Lasmiditan 200 mg co-administered with sumatriptan (Imitrex) 100 mg

The study will be conducted at a single center. Subjects will be randomized using a Williams square design to one of six treatment sequences, as follows:

ABC	ACB
BAC	BCA
CAB	CBA

Seven of the planned 42 subjects will be included in each treatment sequence. The design is balanced for period and first order carryover effects.

Double-blinding will be accomplished as follows:

- Dosing staff, comprised of an unblinded pharmacist or designee (who prepared the medication), an unblinded dosing assistant, and an unblinded registered nurse (RN) will administer all study medications. They will have no other role in the trial and will not communicate their activities in the trial to other staff involved in the trial in any way.
- Investigational product, prepared in the Pharmacy by an unblinded Pharmacist
  or designee, will be dispensed from the Pharmacy in an amber medication vial
  (with a subject specific label blinded to the identity of the investigational
  product) to the unblinded dosing staff and dosed to the subject directly from the
  amber vial to the subject's mouth.
- Prior to dosing, each subject will be blind-folded and will remain blind-folded until the hand and mouth check has been completed. Curtains will be drawn around the bed prior to dosing and will remain in place until the hand and mouth check has been completed. No one will enter the curtained space other than the subject, the unblinded RN, and the unblinded dosing assistant.

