## **Secondary Objective-**

- To compare and contrast the pharmacokinetics of Lasmiditan 200 mg and Sumatriptan (Imitrex) 100 mg administered together to the pharmacokinetics of single doses of either drug administered alone.
- To evaluate the safety and tolerability of Lasmiditan 200 mg and Sumatriptan (Imitrex) 100 mg administered together to the safety and tolerability of single doses of either drug administered alone.
- To compare and contrast the subjective drug effects of Lasmiditan 200 mg and Sumatriptan (Imitrex) 100 mg administered together to the subjective drug effects of single doses of either drug administered alone.

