# 2.2 Study Design

This is a Phase 1, single-center, randomized, double-blind, three-period, cross-over study to investigate the effect of single doses of Sumatriptan (Imitrex) 100 mg on the

pharmacodynamics of single doses of Lasmiditan 200 mg. A total of 42 subjects will be enrolled to ensure at least 36 subjects complete the study with approximately 60% females.

The three dosing periods are as follows-

- A: Lasmiditan 200 mg co-administered with Lasmiditan 200 mg placebo
- B: Sumatriptan (Imitrex) 100 mg co-administered with Lasmiditan 200 mg placebo
- C: Lasmiditan 200 mg co-administered with Sumatriptan (Imitrex) 100 mg

Subjects are randomized using the William square design into one of the six treatment sequences ABC, ACB, BAC, BCA, CAB, CBA.

The study will last approximately 6 weeks including up to 3 weeks for screening and 22 days on study. Screening will be conducted within approximately 21 days of the first dose of study medication. Each dosing period will last 3 days (Day -1, Day 1, and Day 2). A wash-out period of 6 days will take place between each dose. The End of Study Visit (EoS) will take place 5 (+/- 2) days after the third dosing period is completed.

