#### 3. DATA ANALYSIS CONSIDERATIONS

# 3.1 Determination of Sample Size

The sample size calculation for this study is based on the proportion of adverse events in the two treatment groups namely the combination therapy (Lasmiditan + Sumatriptan) vs a single drug (Lasmiditan). The calculation is performed using a test for two proportions in a repeated measures design. To ensure that at least 36 subjects complete, 42 subjects (approximately 60% female) will be enrolled.

The sample size of 36 subjects will provide at least 80% power to show equivalence of the PK of Lasmiditan in the absence and presence of Sumatriptan (Imitrex), assuming a 25% within subject coefficient of variance.

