## 6.4.10.6 Drug Effects Questionnaire (DEQ-5)

The DEQ-5 will be completed as per the protocol. All DEQ-5 data will be provided as a bysubject listing and summarized by period, treatment and visit.

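### The SAP plans no combination-versus-alone difference or interval for the VAS and DEQ-5, although comparing subjective effects is a secondary objective

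*SAP*

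**What the plan says.** The SAP lists among its secondary objectives "To compare and contrast the subjective drug effects of Lasmiditan 200 mg and Sumatriptan (Imitrex) 100 mg administered together", set against the subjective effects of either drug given alone. Protocol 2.2 and the synopsis carry the same objective. The synopsis also lists subjective effects as an exploratory endpoint, "as compared with either drug alone and as measured by results of the VAS scales and the DEQ-5".

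The planned output is one sentence per instrument. SAP 6.4.10.5: "All VAS data will be provided as a by-subject listing and summarized by period, treatment and visit". SAP 6.4.10.6: "All DEQ-5 data will be provided as a bysubject listing and summarized by period, treatment and visit". Neither section names a treatment difference, a model or an interval. Protocol 8.4 to 8.6 contains no VAS or DEQ-5 analysis. Protocol 8.3 permits optional 90% confidence intervals alongside descriptive statistics but defines no contrast between treatments.

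Elsewhere the SAP works differently. Vital signs (6.4.7) and ECG (6.4.10.2) are summarised by treatment and time point with no split by period. For PK (6.4.9.2), combination-to-alone ratios are estimated with 90% intervals.

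**The concern.** The objective asks how the combination differs from each drug alone. The crossover is built to answer that within subjects, yet the planned output stops at descriptive tables. If those tables are split by period, they set different people side by side and show between-subject spread. A reader then has no pre-specified estimate of added sedation or feeling high, and no correct measure of its uncertainty. A real effect could be missed or a chance one over-read. If a contrast is added later, the scale, time point and model would be chosen with the results in view. Protocol 1.2 reports somnolence, dizziness and fatigue as the program's most frequent adverse events, so these scales matter when a second drug is added.

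The display level is also unclear. In the schedule, Visits 2, 3 and 4 are Periods 1, 2 and 3. Taken literally, therefore, *visit* adds nothing to *period*, and the 1, 2, 4 and 8 hour ratings are not named as a summary level.

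**Working it through.** Treatments: A is lasmiditan with placebo, B is sumatriptan with placebo, C is the combination. The contrasts of interest are C−A and C−B.

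**Inputs from the documents**
- Sequences (SAP 2.2): "Subjects are randomized using the William square design into one of the six treatment sequences ABC, ACB, BAC, BCA, CAB, CBA".
- Allocation (Protocol 5.6): "Seven of the planned 42 subjects will be included in each treatment sequence".
- Enrolment (SAP 3.1): "To ensure that at least 36 subjects complete, 42 subjects (approximately 60% female) will be enrolled".

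**Assumptions.** A common SD σ for a single rating and a within-subject correlation ρ of 0.3, 0.5 or 0.7. The documents give neither quantity. σ cancels from the ratios below.

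**1. The plan's own figure.** 42 / 6 = 7 per sequence, as stated. With 36 balanced completers, 36 / 6 = 6 per sequence.

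**2. Cell size if cross-classified.** Each treatment falls in a given period in 2 of the 6 sequences (for example, C is first in CAB and CBA). Each of the nine period-by-treatment cells therefore holds 2 × 7 = 14 subjects, or 2 × 6 = 12 completers. Within a period, the A, B and C cells share no subject.

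**3. One period read alone, against the paired contrast**
- Single-period difference: SE = σ√(2/14) = 0.378σ.
- Paired difference, all subjects: SE = σ√(2(1−ρ)/42).
- Ratio = √(3/(1−ρ)).

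| ρ | single-period SE / σ | paired SE / σ | ratio |
|---|---|---|---|
| 0.3 | 0.378 | 0.183 | 2.07 |
| 0.5 | 0.378 | 0.154 | 2.45 |
| 0.7 | 0.378 | 0.120 | 3.16 |

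With 36 completers the single-period SE is 0.408σ and the paired SEs are 0.197σ, 0.167σ and 0.129σ. The ratios are unchanged.

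**4. All three periods averaged.** With equal cells and complete data, the mean of the three period-specific C−A differences equals the mean of all C ratings minus the mean of all A ratings, which is the mean paired difference. The point estimate is therefore recoverable. The interval is not: the cell SDs describe spread between subjects and carry no information on ρ. Treating the cells as independent gives SE = σ√(2/14)/√3 = 0.218σ. That is 1/√(1−ρ) = 1.20, 1.41 or 1.83 times the paired SE at ρ = 0.3, 0.5 or 0.7.

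**The case against.** Four points weigh against the concern, and each stands in part.

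*Period may be loose wording.* The synopsis, Protocol 5.6 and SAP 2.2 each list the dosing periods as A, B and C, which are treatments. SAP 6.4.9.1 also uses treatment period for the drug given, and SAP 6.1 uses a similar string as a listing order. If period only orders the output, each treatment keeps up to 42 subjects. This stands: cells of 14 follow from the plain reading but are not certain. The contrast is missing on either reading.

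*Nothing is lost.* A reader might infer that the plan throws away the within-subject comparison. It does not. The by-subject listing keeps the paired data, and averaging the period differences returns the point estimate. The ratio of 2.1 to 3.2 describes only someone who reads one period and ignores the other two. What is missing is a pre-specified contrast and its interval.

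*The endpoint is exploratory.* The synopsis labels it so and calls the scales an exploratory safety assessment; SAP 4.3 places them under safety. No hypothesis or power attaches to them, and the SAP departs from no protocol model. This limits the severity and rules out demanding a formal test. It does not remove the objective's request for a comparison.

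*A full set of contrasts would create its own problem.* Post-dose there are 3 VAS × 4 times, 2 VAS × 1 time and 5 DEQ-5 items × 5 times: 12 + 2 + 25 = 39 measures. Two contrasts each give 78 intervals. Peaks on the 8 repeated scales add 16, making 94. This stands, and the remedy should be short.

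**Conclusion.** The gap is real and of moderate importance. A secondary objective asks for a comparison, and the planned output contains no estimate of it and no interval. That conclusion rests on the text alone. The cell sizes of 14 and 12 depend on reading the tables as cross-classified and on full enrolment or balanced completion. The SE ratios (2.1 to 3.2 for one period alone, 1.2 to 1.8 when periods are averaged but treated as independent) also depend on the assumed correlations and a common SD.

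The documents do not support saying that the objective cannot be met, or that period-level tables are wrong in themselves. The data allow the contrast, and period tables can help a reader look for period effects.

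**What to change.** In SAP 6.4.10.5 and 6.4.10.6:

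1. Summarise VAS and DEQ-5 by treatment and time point across periods, as the SAP already does for vital signs and ECG. Period-level tables may stay as supplementary output.
2. Name a few key measures in advance, for example peak sedation, peak high and overall drug liking at 24 hours. For the last, use the 24-hour rating itself, because the pre-dose rating (Protocol 7.9.4) precedes that period's drug.
3. For each, report the within-subject C−A and C−B differences with confidence intervals from a crossover model with period and treatment as fixed effects and subject as random. Label them exploratory, without formal testing.

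Three measures with two contrasts give 6 intervals. The cost is SAP wording and some programming; no new data, visits or subjects are needed. The downside is several unadjusted exploratory intervals, which the report should describe as such.
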